Participants will be followed up for a period of 12 weeks after completion of study treatment. During the follow-up period they will be evaluated in the out-patient setting at 7 ± 1 days, 28 ± 1 days and 12 weeks (± 3 days) after the last dose of the IMP.

There will be two additional follow-up visits (14 ± 1 days and 21 ± 1 days after last caplacizumab dosing) for participants who do not have ADAMTS13 activity levels of $\geq 50\%$ at the time of caplacizumab discontinuation.

A physical exam will be performed, and laboratory tests including platelet count and organ damage markers will be obtained during the visits.

Treatment of a first clinical recurrence (exacerbation or relapse):

Clinical Exacerbation is defined as after a Clinical Response and before a Clinical Remission, platelet count decreases to $<150 \times 10^9/L$ (with other causes of thrombocytopenia excluded), with or without clinical evidence of new or progressive ischemic organ injury, within 30 days of stopping TPE or anti-vWF therapy.

Clinical Relapse is defined as after a Clinical Remission, platelet count decreases to $<150 \times 10^9/L$ (with other causes of thrombocytopenia ruled out), with or without clinical evidence of new ischemic organ injury. A Clinical Relapse must be confirmed by documentation of severe ADAMTS13 deficiency ($<10\%$).

In case of a first clinical recurrence (exacerbation or relapse) of the presenting TTP episode during the overall study period, it is up to the Investigators to adjust the ongoing treatment plan, which may include start or restart of TPE and adjustment of IST regimen and caplacizumab therapy. In case that caplacizumab treatment is maintained for a first clinical recurrence (exacerbation or relapse), the visit schedule will be the same as during the initial treatment period.

If a participant develops a second clinical recurrence (exacerbation or relapse) the participant will discontinue from the study ([Section 7.1.1](#)). At the time of discontinuing from the study, if possible, an early discontinuation visit should be conducted, as shown in the SoA ([Section 1.3](#)). See SoA for data to be collected at the time of study discontinuation and follow-up and for any further evaluations that need to be completed.

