4.4 END OF STUDY DEFINITION

A participant is considered to have completed the study if he/she has completed all periods of the study including the last scheduled procedure shown in the Schedule of Activities ([Section 1.3](#)).

The end of the study is defined as the date of the last visit of the last participant in the study or last scheduled procedure shown in the Schedule of Activities for the last participant in the trial.

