1 INTRODUCTION

1.1 STUDY DESIGN

This is an open-label, single-arm, Phase 3, multicenter study to evaluate the efficacy and safety of caplacizumab and immunosuppressive therapy (IST) without first-line therapeutic plasma exchange (TPE) in adults with immune-mediated thrombotic thrombocytopenic purpura (iTTP).

The anticipated study duration per participant, without a recurrence while on therapy, is a maximum of approximately 24 weeks (ie, approximately 1 day for screening + maximum 12 weeks of treatment for the presenting episode + 12 weeks of follow-up). All participants will receive open-label caplacizumab daily until sustained disintegrin and metalloproteinase with a thrombospondin type 1 motif13 (ADAMTS13) activity normalization ($\geq 50\%$) is achieved at 2 consecutive visits, after platelet count normalization (defined as $\geq 150 \times 10^9/L$ for 2 consecutive values) or 12 weeks of caplacizumab treatment, whichever occurs first.

For participants who experienced a first clinical recurrence (exacerbation or relapse) during the overall study period, the ongoing treatment plan may be adjusted including a start or re-start of TPE and adjustment of IST regimen and caplacizumab therapy. In case that caplacizumab treatment is maintained for a first clinical recurrence, the visit schedule will be the same as during the initial treatment period.

[figure not shown]
The primary analysis will be conducted after study completion of all participants, ie, when all the participants will have discontinued from the study.

In addition, an interim analysis (IA) will be conducted after the first 30 participants with baseline ADAMTS13 activity of $<10\%$ have completed the study (eg ended treatment period per protocol and completed the follow-up period of 12 weeks) (see [Section 3.8](#) for further details). A Data Monitoring Committee (DMC), independent from the Sponsor, will be appointed to monitor the safety and the scientific integrity of this study on an on-going basis, and to provide in a timely fashion appropriate recommendations to the Sponsor.

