1.2.1 Estimands

Primary estimand defined for the primary endpoint is summarized in [Table 2](#). More details are provided in [Section 3.2](#).

Table 2 - Summary of primary estimand for main endpoints

Endpoint Category (estimand)	Estimands			
	Endpoint	Population	Intercurrent event(s) handling strategy	Population-level summary (Analysis and missing data handling)
Primary objective: To evaluate the efficacy of caplacizumab in combination with immunosuppressive therapy (IST) without therapeutic plasma exchange (TPE) in adults with immune mediated thrombotic thrombocytopenic purpura (iTTP)				
Primary endpoint (treatment policy estimand)	Remission	All enrolled participants who received at least 1 dose of IMP and with an ADAMTS13 activity <10% at baseline	Regardless of adherence to study intervention and/or study discontinuation	Proportion of participants achieving Remission without requiring TPE during the overall study period

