3.8 INTERIM ANALYSES

An interim analysis will be performed after the first 30 participants with baseline ADAMTS13 activity of <10% have completed treatment period per protocol and 12 weeks of follow-up. The participants who have completed the study at the time of IA will be included in the interim analysis.

The IA will provide a preliminary assessment of the efficacy and safety of Caplacizumab and immunosuppression without first-line TPE in adults with iTTP. The study will continue enrollment through this IA and the interim results should not alter the study conduct, ie, there is not a plan for early termination of the study based on this IA.

In addition, a DMC will be appointed to monitor the safety of the patients enrolled in the study on an ongoing basis in order to provide timely recommendations to the Sponsor. The purpose of this is to ensure the clinical data integrity and the appropriate final interpretation of the study results. At each DMC meeting during the conduct of the trial (approximately every 6 months), the DMC makes a recommendation to the Sponsor to continue the trial as planned, or with an amendment, or to terminate the trial. Further details regarding the DMC are included in the DMC charter.

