5.2 APPENDIX 2 PARTICIPANT DISPOSITIONS

The number (%) of participants included in each of the analysis populations listed in [Table 3](#) will be summarized.

Screen failures are defined as participants who consent to participate in the study but are not subsequently enrolled. The number (%) of screen failures and reasons for screen failures (ie, eligibility criteria not met) will be provided on the screened population (participants who did the screening visit).

The number (%) of participants in the following categories will be provided:

- Enrolled participants
- Enrolled but not exposed participants
- Enrolled and exposed participants
- Participants who completed the study treatment period as per protocol
- Participants who did not complete the study treatment period as per protocol and main reason for premature end of treatment
- Participants who completed the study as per protocol (*Completion of End of Study/Follow-up* form: “Did the subject complete the study?” equal to Yes)
- Participants who did not complete the overall study period as per protocol and main reason for premature end of study

In addition, the number (%) of participants screened-failed, enrolled, with premature end of treatment and with early study discontinuation will be provided by country and site.

Protocol deviations

Critical and major protocol deviations (automatic or manual) will be summarized on the enrolled population.

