- The values resulting from these derivations will be the values used for the graphical representation of platelet, LDH and ADAMTS13 activity from Day 4.

Consecutive laboratory assessments are considered as 'consecutive visits' for efficacy endpoints.

A participant could potentially have missing laboratory assessment data, however, remission could still be confirmed at a subsequent laboratory value. In the case there is inadequate information to determine the remission status of a participant by the end of the study, the participant will be treated as not having achieved remission.

Clinical evidence of new or progressive ischemic organ injury

Clinical evidence of new or progressive ischemic organ injury is defined as any presence of following clinically significant iTTP event:

- Neurological event
- Elevated cardiac troponins
- Acute myocardial infarction
- Conduction abnormality
- Repolarization abnormality
- Heart failure
- Clinically significant renal event

which will be identified from the checkboxes in the "Clinically Significant TTP Event" eCRF form.

Exacerbation of TTP, Relapse of TTP and Other event will not be considered as clinical evidence of new or progressive ischemic organ injury.

Sustained Clinical Response

Sustained Clinical response is defined by the concomitance of the 3 following criteria for at least 2 consecutive visits (starting from D2):

- platelet count $\geq 150 \times 10^9/L$
- LDH $< 1.5 \times ULN$
- no clinical evidence of new or progressive ischemic organ injury

Remission

Remission is defined as (1) a sustained Clinical response (see above) associated with (2) Clinical remission or (3) Complete ADAMTS13 Remission, whichever occurs first, and defined as:

- Clinical remission: No TPE (*Plasma Exchange* form) and no anti-VWF therapy (Caplacizumab treatment) for ≥ 30 days (from the date that Clinical Response is achieved).
- Complete ADAMTS13 Remission: The attainment of ADAMTS13 activity level $\geq 50\%$ for at least 2 consecutive visits (starting from D2).

Time to event

For each of below time to event, in case of no observation of the event or death, the censoring date will be defined as the last non-missing value of the analyzed parameter (platelet count, LDH....) if any, else as the start date of treatment (defined as first caplacizumab administration [whatever marketed or study IMP]).

- Time to platelet count response will be calculated as follow:

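### The interim set in SAP 3.8 is limited to participants who completed the study; as defined, that leaves out early exits and does not match the primary estimand

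*SAP*

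**What the plan says.** The interim is triggered by the first 30 participants with baseline ADAMTS13 activity below 10% who have finished treatment and 12 weeks of follow-up (Protocol 9.3, SAP 3.8). Protocol 9.3 leaves further detail to the SAP. For who is analysed, SAP 3.8 says: "The participants who have completed the study at the time of IA will be included in the interim analysis".

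Four places bear on what completing the study means:
- Protocol 4.4: "A participant is considered to have completed the study if he/she has completed all periods of the study", including the last scheduled procedure.
- SAP 1.1, on the interim: participants who "have completed the study (eg ended treatment period per protocol and completed the follow-up period of 12 weeks".
- SAP 5.2: completers are those whose eCRF completion question is answered Yes. A separate line counts "Participants who did not complete the overall study period as per protocol and main reason for premature end of study".
- SAP 1.1, on the timing of the primary analysis: study completion of all participants, "ie, when all the participants will have discontinued from the study".

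On early exits, Protocol 4.1 states: "If a participant develops a second clinical recurrence (exacerbation or relapse) the participant will discontinue from the study". Protocol 7.2 and 7.3 provide for withdrawal and loss to follow-up.

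The primary estimand (SAP 1.2.1, Table 2) covers all dosed participants with baseline ADAMTS13 below 10%: "Regardless of adherence to study intervention and/or study discontinuation". Where remission status cannot be determined by the end of the study, SAP 5.4 says "the participant will be treated as not having achieved remission".

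**The concern.** The only definition of participant completion in the two documents is Protocol 4.4. Under it, and under the SAP 5.2 eCRF field, a participant who dies, withdraws, is lost or leaves at a second recurrence has not completed the study and so does not enter the interim set. The set is then selected on the event that the estimand says to disregard. It also removes many of the participants for whom the SAP 5.4 non-remission rule was written.

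At stake is whether the interim remission rate can be read as an early look at the final one. A reader would take the two as the same quantity at two times. On the completers' rule they have different denominators. The trial is open-label, so if the set is settled only at the data cut, it could be settled knowing who left and how they fared.

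**Working it through.** **1. The plan's own figure.** SAP section 4 assumes a 70% responder rate, from 85% remission and 18% requiring TPE: 0.85 × (1 − 0.18) = 0.697. With N = 55, 0.70 × 55 = 38.5, rounded up to 39. The 95% Wilson limits are

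[p + z²/2n ± z√(p(1−p)/n + z²/4n²)] / (1 + z²/n), with z = 1.96.

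For 39/55 the lower limit is 57.9%, which matches the stated 58%. This figure is not in dispute; the point concerns the interim set only.

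**2. Who is counted under each reading.**

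| Participant at the data cut | Completers (Protocol 4.4, SAP 5.2) | Participation ended (SAP 1.1, primary-analysis wording) | Final analysis (SAP 1.2.1, 5.4) |
|---|---|---|---|
| Finished all periods | in | in | in |
| Died before the final visit | out | in | in |
| Withdrew or lost | out | in | in |
| Left at a second recurrence | out | in | in |

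Only the second reading agrees with the final analysis.

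**3. Size for a given exit fraction.** The documents give no exit rate, and Protocol 7.2 expects withdrawal to be uncommon, so every exit fraction here is an assumption. Hold the overall mITT rate at 0.70. Let a fraction d exit early, with response rate x among them. Then

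completers' rate = (0.70 − d·x) / (1 − d).

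| d (assumed) | x = 0 | x = 1 | Difference from 70%, in points |
|---|---|---|---|
| 3% | 0.70/0.97 = 72.2% | 0.67/0.97 = 69.1% | +2.2 to −0.9 |
| 5% | 0.70/0.95 = 73.7% | 0.65/0.95 = 68.4% | +3.7 to −1.6 |
| 10% | 0.70/0.90 = 77.8% | 0.60/0.90 = 66.7% | +7.8 to −3.3 |

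The difference is zero at x = 0.70.

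**4. Size in counts.** Take 21 responders among 30 completers and add k early exits (95% Wilson intervals in brackets).

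| k (assumed) | No exit responded | All exits responded |
|---|---|---|
| 0 | 21/30 = 70.0% (52.1–83.3) | 21/30 = 70.0% (52.1–83.3) |
| 1 | 21/31 = 67.7% (50.1–81.4) | 22/31 = 71.0% (53.4–83.9) |
| 2 | 21/32 = 65.6% (48.3–79.6) | 23/32 = 71.9% (54.6–84.4) |
| 4 | 21/34 = 61.8% (45.0–76.1) | 25/34 = 73.5% (56.9–85.4) |

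Two exits move the rate by 4.4 points one way (70.0 − 65.6) or 1.9 the other (71.9 − 70.0). The half-width of the interval for 21/30 is (83.3 − 52.1)/2 = 15.6 points, so each shift shown lies within the interim sampling error.

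**5. Direction.** Early deaths and withdrawals would tend to be non-responders, and leaving them out raises the rate. A clinical relapse, however, by definition follows Clinical Remission (SAP 5.4). A participant who leaves at a second recurrence that is a relapse has therefore already remitted, and is a responder if no TPE was needed. Leaving that participant out lowers the rate. The sign depends on the mix.

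**The case against.** The strongest reply is that the inclusive reading is what the SAP means. SAP 1.1, just before its interim text, equates study completion with everyone having left the study. The interim example there begins with eg, and SAP 3.8 does not say only. Since enrolment continues through the interim, the sentence may simply separate finished from ongoing participants. The mITT definition, the non-remission rule and the Safety population all exist already, and SAP 3.8 does not expressly set them aside.

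Much of this stands: inclusive intent is plausible. But the looser wording concerns when the primary analysis is run. It does not define the interim set, and the one formal definition, together with the eCRF field a programmer would use, points the other way.

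It also stands that no decision rests on the interim. There is no hypothesis test or success criterion (SAP 3.1), and SAP 3.8 says the results should not alter study conduct and plans no early termination on them.

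Three stronger readings are tempting, and the documents do not support them:
- *The interim rate is inflated.* The direction is not fixed (step 5), and no exit rate is given.
- *On-study deaths would disappear from the interim safety report.* SAP 3.6 and Protocol 9.2.6 make the Safety population the default, and SAP 3.6.2 tabulates deaths. SAP 3.8 leaves unsaid whether its sentence overrides that default, which calls for confirmation only. DMC and sponsor safety review continue separately (Protocol 10.1.5.1).
- *The Protocol 9.3 trigger must change.* The trigger governs when the interim is run. Who is analysed can be settled in the SAP.

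**Conclusion.** The point holds as a mismatch in a stated rule, at low severity. Applied as written, SAP 3.8 yields a completers' interim set, while the final analysis follows the treatment-policy estimand with non-remission for undetermined status. The two rates would not estimate the same quantity.

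The size cannot be derived from the documents. Under assumed exit fractions of 3% to 10% and the 70% planning rate, the interim rate would differ from the estimand-consistent rate by between +7.8 and −3.3 points. The low end of that range fits better with Protocol 7.2's expectation that withdrawal is uncommon. How many participants would count as non-completers is itself unsettled: Protocol 7.1.1 describes follow-up after permanent discontinuation of caplacizumab both as ending with the 28-day visit and as running to the scheduled end of study.

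The consequence is confined to a descriptive interim report; the final analysis is not affected.

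**What to change.** In SAP 3.8:
- State that interim efficacy includes all mITT participants who, by the data cut, have completed the study or ended it prematurely for any reason, with the SAP 5.4 rule applied so that undetermined status counts as non-remission.
- Preferably restrict this to participants enrolled up to a fixed cut-off. Without one, recent enrollees can enter the set only by leaving early, because completion can take about 24 weeks, so early exits would be over-represented.
- Confirm that the inclusion sentence does not remove participants who died or left early from the interim safety summaries.

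The cost is a few sentences in the SAP, with no new data and no change to the Protocol 9.3 trigger. The interim rate may be slightly less favourable. If the cut-off is used, completers enrolled after it wait for the final analysis.

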4 SAMPLE SIZE DETERMINATION

The primary endpoint is the proportion of participants achieving remission without requiring TPE during the overall study period. The responder rate will be estimated, and no pre-specified success criterion and formal statistical hypothesis testing is planned.

An adequate number of participants will be enrolled to ensure at least 55 participants with ADAMTS13 activity levels of <10% at baseline is available for analysis of the primary endpoint (mITT analysis).

With the sample size of 55 participants, assuming the true responder rate of participants who achieve remission without requiring TPE during the overall study period is 70% (ie, overall, 85% remission rate and 18% of participants requiring TPE), the lower bound of 95% Wilson confidence interval (CI) would be 58%.

Table 6 - Lower bound of 95% confidence interval given various assumed rates of participants achieving Remission without requiring TPE during the overall study period

Assumed responder rate	Lower bound of 95% Confidence Interval of responder rate*
65% or below	At most 52%
70%	58%
75%	64%
80%	68%
85% or greater	At least 74%

* In post-hoc analysis of HERCULES, the upper confidence limit of remission rate for the placebo arm (placebo + IST + TPE) was 54%. HERCULES (ALX0681-C301) was a Phase III, randomized, double-blind, placebo-controlled, study to evaluate the efficacy and safety of caplacizumab when administered in addition to standard of care treatment in subjects with an acute episode of acquired TTP.

5 SUPPORTING DOCUMENTATION

5.1 APPENDIX 1 LIST OF ABBREVIATIONS

ADAMTS13:	disintegrin and metalloproteinase with a thrombospondin type 1 motif13
AE:	adverse event
AESI:	adverse event of special interest
ALT:	alanine transaminase
aPTT:	activated partial thromboplastin time
AST:	aspartate aminotransferase
ATC:	anatomical therapeutic chemical
BMI:	body mass index
BSA:	body surface area
BUN:	blood urea nitrogen
CDR:	complementary determining region
CI:	confidence interval
COVID:	coronavirus disease
cTnI:	cardiac troponin I
DMC:	data monitoring committee
ECG:	electrocardiogram
e-CRF:	electronic case report form
<hr/>	
FAS:	full analysis set
FU:	follow-up
HBsAg:	hepatitis B surface antigen
hCG:	human chorionic gonadotropin
<hr/>	
HIV:	human immunodeficiency virus
HLGT:	high-level group term
HLT:	high level term
IA:	interim analysis
ICF:	inform consent form
ICU:	intensive care unit
IMP:	investigational medicinal product
IST:	immunosuppressive therapy
iTPP:	immune mediated thrombotic thrombocytopenic purpura
LDH:	lactate dehydrogenase
LLN:	lower limit of normal
LLOQ:	lower limit of quantitation/detection limit
LLT:	lower-level term
mADA:	modified anti-drug antibody
MCH:	mean corpuscular hemoglobin
MCHC:	mean corpuscular hemoglobin concentration

MCS:	mental component summary
MCV:	mean corpuscular volume
MedDRA:	medical dictionary for regulatory activities
mITT:	modified ITT
MRD:	minimal required dilution
MSR:	minimum significant ratio
NAb:	alternative neutralizing antibody

PCS:	physical component summary
PCSA:	potentially clinically significant abnormality
PD:	pharmacodynamic
PK:	pharmacokinetic
PQAT:	patient's qualitative assessment of treatment
pre-Ab:	pre-existing antibody
PT:	preferred term
Q1:	first interquartile range 1
Q3:	third interquartile range
RBC:	red blood cell
RICO:	ristocetin cofactor
SAE:	serious adverse event
SAP:	statistical analysis plan
SD:	standard deviation
SF-12:	short form 12-item survey
SMQ:	standardized MedDRA query
SOC:	system organ class
TCP:	titration cut-point
TE:	treatment-emergent
TEAE:	treatment-emergent adverse event
TPE:	therapeutic plasma exchange
TTP:	thrombotic thrombocytopenic purpura
ULN:	upper limit of normal
ULOQ:	upper limit of quantitation/detection limit
WBC:	white blood cells
WHO-DD:	world health organization-drug dictionary

5.2 APPENDIX 2 PARTICIPANT DISPOSITIONS

The number (%) of participants included in each of the analysis populations listed in [Table 3](#) will be summarized.

Screen failures are defined as participants who consent to participate in the study but are not subsequently enrolled. The number (%) of screen failures and reasons for screen failures (ie, eligibility criteria not met) will be provided on the screened population (participants who did the screening visit).

The number (%) of participants in the following categories will be provided:

- Enrolled participants
- Enrolled but not exposed participants
- Enrolled and exposed participants
- Participants who completed the study treatment period as per protocol
- Participants who did not complete the study treatment period as per protocol and main reason for premature end of treatment
- Participants who completed the study as per protocol (*Completion of End of Study/Follow-up* form: “Did the subject complete the study?” equal to Yes)
- Participants who did not complete the overall study period as per protocol and main reason for premature end of study

In addition, the number (%) of participants screened-failed, enrolled, with premature end of treatment and with early study discontinuation will be provided by country and site.

Protocol deviations

Critical and major protocol deviations (automatic or manual) will be summarized on the enrolled population.

